WHO-DD:	world health organization-drug dictionary

1 OVERVIEW AND INVESTIGATIONAL PLAN

1.1 STUDY DESIGN AND RANDOMIZATION

This study is an open-label, 1:1 randomized, active-controlled, 26-week duration, parallel-group, multicenter, US-only, Phase 3b study to compare the efficacy and safety of Soliqua 100/33 with Lantus overall and in ethnically/racially diverse groups with T2DM inadequately controlled on basal insulin and 1 or 2 OAD agents. The patients will be randomized according to their self-reported ethnicity/race (i.e., Hispanics of any race, non-Hispanic black/African Americans and non-Hispanic Asians). Additionally, to ensure a balanced IMP allocation, randomization will be stratified by their screening HbA1c value ($<8.5\%$ versus $\geq 8.5\%$), the background use of SGLT-2 inhibitors (yes/no) and the background use of SUs (yes/no). Patients will participate in 1 of 2 ways, either at a traditional 'brick & mortar' investigational site, or fully remotely through a virtual arrangement.

The study will consist of 3 periods:

- An up to 2-week screening period
- A 26-week open-label randomized treatment period: at the end of the screening period (Week 0, Visit 2) patients will be randomized to receive either Soliqua 100/33 or Lantus
- A 3-day post-treatment safety follow-up period (not required for patients who prematurely and permanently discontinued IMP administration but stayed in the study through Week 26; these patients should continue all study visits except for the follow-up visit).

1.2 OBJECTIVES

1.2.1 Primary objectives

- To demonstrate the superiority of Soliqua 100/33 versus Lantus in the HbA1c change from baseline to Week 26 within the overall population.
- To demonstrate the benefit of Soliqua 100/33 versus Lantus in the HbA1c change from baseline to Week 26 within each ethnic/racial subgroup evaluated (i.e., Hispanics of any race, non-Hispanic black/African Americans and non-Hispanic Asians).

1.2.2 Secondary objectives

- To assess the effects of Soliqua 100/33 versus Lantus on the secondary efficacy parameters to Week 26 for the selected endpoint within each ethnic/racial subgroup evaluated.
- To assess the change from baseline to Week 26 in daily insulin glargine dose within each ethnic/racial subgroup.
- To evaluate the safety and tolerability (egg, gastrointestinal tolerability) of Soliqua 100/33 versus Lantus to Week 26 within each ethnic/racial subgroup.

[figure not shown]
1.2.3 Other objectives

- To assess the effects of Soliqua 100/33 versus Lantus on other efficacy parameters to Week 26 for the selected endpoint within each ethnic/racial subgroup evaluated.
- To assess the effects of Soliqua 100/33 versus Lantus on efficacy and safety parameters to Week 26 in the overall population.
- To evaluate and compare the effect of Soliqua 100/33 versus Lantus on Patient Reported Outcome (PRO) measures to Week 26 within each ethnic/racial subgroup.

1.3 DETERMINATION OF SAMPLE SIZE

Due to difficulty in recruitment, it has been decided to terminate the trial early, leading to a total sample size of 240 patients (120 per treatment), for which efficacy and safety of Soliqua 100/33 and Lantus will be evaluated using descriptive statistics.

1.4 STUDY PLAN

R = Randomization; patients will continue their background OADs at stable doses throughout the study; background basal insulin will be stopped and replaced with the IMP.

a: Stratified by (1) ethnicity/race, (2) HbA1c at visit 1, (3) background use of SGLT2 inhibitors and (4) background SU use.

b: A sub-set of patients only.

= Remote visit (telephone or videoconference) for all sites = On-site (in person) visit for brick-and-mortar sites/ remote visit (telephone or videoconference) for fully-remote sites

1.5 MODIFICATIONS TO THE STATISTICAL SECTION OF THE PROTOCOL

Table 1 - Protocol amendment statistical changes

Amendment Number	Date Approved	Rationale	Description of statistical changes
01	18-Dec-2017	Removal of extension secondary/other efficacy endpoints	Removal of all analysis related to the extension phase Order of secondary efficacy endpoint testing hierarchy was changed according to the current list of secondary efficacy endpoints.

1.6 STATISTICAL MODIFICATIONS MADE IN THE STATISTICAL ANALYSIS PLAN

The statistical analysis plan history table below gives the timing, rationale, and key details for major changes to the statistical analysis features in the statistical analysis plan.

Table 2 – Statistical analysis plan statistical changes

SAP version number	Date approved	Rationale	Description of statistical changes
This version		FDA statistical comments	Safety analysis added: AEs and AESIs summarized over the whole on-study period (on-treatment and post-treatment)
This version		sponsor strategic decision of trial early termination	Changes on sample size and efficacy endpoint analyses
This version			Minor changes in lab test

2 STATISTICAL AND ANALYTICAL PROCEDURES

2.1 ANALYSIS ENDPOINTS

The endpoints listed in this section correspond to the originally planned endpoints collected per protocol. Only the critical endpoints will be analyzed with more details in [Section 2.4](#).

2.1.1 Demographic and baseline characteristics

The baseline value is defined as the last available value prior to the first dose administration of investigational medicinal product (IMP) or the last available value on or before the date of randomization if not treated with IMP.

All baseline safety parameters are presented along with the summary statistics in the safety section ([Section 2.4.5](#)). Baseline efficacy parameters are provided as part of the baseline characteristics, in addition to efficacy summaries in the efficacy section ([Section 2.4.4](#)).

Demographic characteristics

Demographic characteristics to be summarized are:

- Age (years) derived as: $(\text{Date of informed} - \text{Date of birth})/365.25$,
- Age categories (<50 , ≥ 50 to <65 , ≥ 65 to <75 , ≥ 75 years),
- Gender (Male, Female),
- Self-reported ethnicity/race (Hispanics of any race, non-Hispanic black/African Americans, and non-Hispanic Asians)),
- HbA1c (%) at Screening,
- FPG at screening,
- Body weight at screening,
- BMI at screening,
- Randomization strata of HbA1c ($<8.5\%$, $\geq 8.5\%$) at Screening,
- Randomization strata of background use of SGLT-2 inhibitors (yes, no) at Screening,
- Randomization strata of background use of sulfonylureas (yes, no) at Screening,
- Baseline body mass index (BMI) (kg/m^2) derived as: $(\text{Weight in kg})/(\text{Height in meters})^2$,
- Baseline BMI categories (<30 , $\geq 30 \text{ kg/m}^2$),

Medical or surgical history

Medical history and medical findings include:

- Medical or surgical history,
- Family allergy history,
- Diabetes history information,
- Diabetes complication history,
- Alcohol habits,
- Tobacco smoking habits.

Medical and surgical history will be coded to a “lower level term (LLT)”, “preferred term (PT)”, “high level term (HLT)”, “high level group term (HLGT)”, and associated primary “system organ class (SOC)” using the version of Medical Dictionary for Regulatory Activities (MedDRA) currently in effect at Sanofi at the time of database lock.

Disease characteristics at baseline

Diabetes history includes:

Duration of diabetes (years) derived as: (Date of informed consent – Date of diagnosis of diabetes + 1)/365.25,

- Duration of diabetes categories: (<10, ≥10 years)
- Age at onset of diabetes (years) derived as: Year of diagnosis of diabetes – Year of birth,
- Type of OADs at Screening
- Type of basal insulin at screening
- History of gestational diabetes (Yes, No)
- Baseline diabetic complications (Yes, No to Diabetic retinopathy, Diabetic neuropathy, and Diabetic nephropathy)
- eGFR at screening (mL/min/1.73m²),
- eGFR categories at screening (<15 mL/min/1.73m² [End stage renal disease], ≥15 to <30 mL/min/1.73m² [Severe decrease in GFR], ≥30 to <60 mL/min/1.73m² [Moderate decrease in GFR], ≥60 to <90 mL/min/1.73m² [Mild decrease in GFR], and ≥90 mL/min/1.73m² [Normal]).

2.1.2 Prior or concomitant medications

All medications taken within 6 months before the screening visit and until the end of the study are to be reported in the electronic case report form (eCRF).

All medications will be coded using the World Health Organization-Drug Dictionary (WHO-DD) using the version currently in effect at Sanofi at the time of database lock.

- Prior medications are those the patient used prior to first administration of IMP. Prior medications can be discontinued before first administration or can be ongoing during treatment phase.
- Concomitant medications are any treatments received by the patient concomitantly to the IMP, from the 1st administration of IMP to the date of last administration + 3 days. A given medication can be classified both as a prior medication and as a concomitant medication.
- Post-treatment medications are those the patient took (continued or initiated) in the period running from the 4th day after the last administration of IMP up to the end of the study.

Rapid acting insulin (glulisine) is suggested as rescue therapy and it should be started as a once-daily regimen administered prior to the main meal of the day (excluding breakfast). If, according to the Investigator's judgement, rapid-acting insulin is not in the best interest of the patient, addition of an OAD (within the category of permitted background medications) or increases in the OAD doses already taken by the patient (according to the local label) may be considered as a secondary option for rescue therapy.

Note: GLP-1 receptor agonists are not permitted as rescue therapy.

After these assessments are completed and rescue therapy is initiated, the patient should remain in the study and continue to administer the study treatment (including background therapy). The planned visits and assessments should be performed until the last scheduled visit.

The following drugs are not permitted during the screening period or the treatment periods of the study:

- Any type of glucose-lowering agents other than the IMP (including insulins or OADs), authorized background anti-diabetic therapy and rescue therapy, if necessary;

Note:

- Short-term use (≤ 10 days) of short/rapid-acting insulin due to acute illness or surgery (e.g., infectious disease) is allowed;
 - If, according to the Investigator's judgment, rapid-acting insulin is not in the best interest of the patient, dose increases for concomitant OADs (except for up-titration of SUs) to manage uncontrolled hyperglycemia will be considered rescue therapy.
- Systemic (i.e., oral or injectable) glucocorticoids for more than 7 days, whereas topical or inhaled applications are allowed with no time limit;

Any weight-loss medication, if applicable, should be maintained at a stable dose throughout the study duration.

2.1.3 Efficacy endpoints

All efficacy measurements collected during the study will be considered for analyses, including those obtained after IMP discontinuation or introduction of rescue therapy. Patients requiring rescue are identified as those with the reason for treatment ticked “rescue therapy” in e-CRF “Medication” page.

HbA1c, 2-hour PPG, FPG, glucose excursions are measured/calculated in a central laboratory (see study flowchart in [Appendix C](#)). Body weight, SBP and DBP are measured at on-site visits by the investigator or at the local testing center for subjects enrolled in the virtual sites. Efficacy variables will be summarized in both standard international units and conventional units when applicable.

Standardized meal test

A subset of randomized patients per treatment arm/race/ethnic group will undergo a standardized meal challenge to assess fasting and postprandial glucose (tested at a central laboratory), as well as the postprandial glycemic excursion, as part of the screening procedures and during Week 26.

In case of permanent discontinuation of treatment with IMP, the standardized meal test should be performed only if the patient receives treatment on the day of the visit. The meal test should also be performed at the end of study as planned.

If the patient drops out of the study, at the time of IMP discontinuation, regardless of whether the patient received IMP or not on the day of the meal test, the meal test should be performed.

Blood for plasma glucose is drawn 5 times:

- 30 minutes prior to the start of the meal (during Screening and at end-of-treatment for patients randomized to the Lantus PM dosing group) or before IMP administration (at Week 26 for the Soliqua 100/33 arm and for the Lantus AM dosing group);
- Just before the start of the standardized meal (Minute 0), at least 30 minutes after the Soliqua or Lantus AM dosing injection;
- 30 minutes after the start of the standardized meal;
- 60 minutes after the start of the standardized meal;
- 120 minutes after the start of the standardized meal.

Patients who are participating as part of the designated virtual study model will complete this meal test at a local laboratory testing facility.

Observation period

The on-treatment period for primary and other efficacy variables is defined as the time from the first injection of open-label IMP up to 14 days for HbA1c; 0 days for standardized meal test parameters and SMPG and insulin glargine dose; 1 day for FPG; and 3 days for body weight after the last injection of IMP or up to the introduction of rescue therapy, whichever is the earliest.

2.1.3.1 Primary efficacy endpoint(s)

The primary efficacy endpoint is the change from baseline to Week 26 in HbA1c (%).

Blood samples for HbA1c measurements will be collected at Screening and at study time points listed in study flow chart and will be measured at a central laboratory.

If a patient needs to receive rescue antidiabetic medication or if a decision to permanently discontinue the IMP is made, an assessment of HbA1c should be performed before the introduction of rescue medication/permanent discontinuation. Following introduction of rescue medication, the patient should continue in the study and all study procedures according to the protocol should be performed.

2.1.3.2 Secondary efficacy endpoint(s)

- Percentage (%) of patients achieving the HbA1c target of <7% at Week 26
- Change in 2-hour postprandial glucose (PPG) as measured utilizing a standardized meal test at Week 26 (for patients that performed the standardized meal test)
- Change in 2-hour glycemic excursions as measured utilizing a standardized meal test at Week 26 (for patients that performed the standardized meal test)
- Change from baseline to Week 26 in daily insulin glargine dose
- Change from baseline to Week 26 in body weight

2.1.3.3 Other efficacy endpoints

- HbA1c change from baseline to Week 12
- Fasting plasma glucose change from baseline to Week 26
- Percentage of patients requiring rescue therapy by Week 26
- Percentage of patients reaching the HbA1c target of <7% at Week 26 with no body weight gain
- Percentage of patients reaching the HbA1c target of <7% at Week 26 with no documented symptomatic hypoglycemia (SMPG ≤ 70 mg/dL [3.9 mmol/L])
- Percentage of patients reaching the HbA1c target of <7% at Week 26 with no documented symptomatic hypoglycemia (SMPG <54 mg/dL [3.0 mmol/L])
- Percentage of patients reaching the HbA1c target of <7% at Week 26 with no body weight gain and no documented symptomatic hypoglycemia (SMPG ≤ 70 mg/dL [3.9 mmol/L])
- Percentage of patients reaching the HbA1c target of <7% at Week 26 with no body weight gain and no documented symptomatic hypoglycemia (SMPG <54 mg/dL [3.0 mmol/L])
- PRO measures

2.1.4 Safety endpoints

The safety analysis will be based on the reported adverse events, hypoglycemia, and other safety information, such as clinical laboratory data, and vital signs, etc.

Observation period

The observation period for safety data will be divided into 3 segments:

- The pre-treatment period is defined as the time between the date of signing of the informed consent (inclusive) and the first injection of IMP (exclusive),
- The on-treatment period is defined as the time from the first injection of IMP (inclusive) up to and including 3 days after the last injection of IMP (treatment-emergent AE [TEAE] period),
- The post-treatment period is defined as the time starting 4 days after last injection of IMP (after the TEAE period).

2.1.4.1 Hypoglycemia

Hypoglycemia will be identified as events recorded on the dedicated e-CRF “Hypoglycemic event information” page, and will be categorized as follows (see study protocol for further details):

Severe hypoglycemia

Severe hypoglycemia is an event requiring assistance of another person to actively administer carbohydrate, glucagon, intravenous glucose or other resuscitative actions. These episodes may be associated with sufficient neuroglycopenia to induce seizure, unconsciousness or coma. Plasma glucose measurements may not be available during such an event, but neurological recovery attributable to the restoration of plasma glucose to normal is considered sufficient evidence that the event was induced by a low plasma glucose concentration.

Severe hypoglycemia is identified in e-CRF “Hypoglycemic event” page as those documented as,

- To the question “Countermeasure Administration”, ticked the option “Subject was Not Capable of Treating Self and Required Assistance”, and
- To the question “Were Symptoms Present”, ticked “Yes”.

Documented hypoglycemia with plasma glucose cut-off of ≤ 70 mg/dL (3.9 mmol/L)

Documented hypoglycemia with plasma glucose cut-off of ≤ 70 mg/dL (3.9 mmol/L) is any hypoglycemia documented by a measured plasma glucose concentration of ≤ 70 mg/dL (3.9 mmol/L); and is identified in e-CRF “Hypoglycemic event” page as those documented as,

- To the question “Any Hypoglycemic Events Experienced”, ticked “Yes”, and
- With a plasma glucose value before countermeasure ≤ 70 mg/dL (3.9 mmol/L).

Documented hypoglycemia with plasma glucose cut-off of <54 mg/dL (3.0 mmol/L)

Documented hypoglycemia with plasma glucose cut-off of <54 mg/dL (3.0 mmol/L) is any hypoglycemia documented by a measured plasma glucose concentration of <54 mg/dL (3.0 mmol/L); and is identified in e-CRF “Hypoglycemic event” page as those documented as,

- To the question “Any Hypoglycemic Events Experienced”, ticked “Yes”, and
- With a plasma glucose value before countermeasure <54 mg/dL (3.0 mmol/L).

Pseudo hypoglycemia

Pseudo hypoglycemia is an event during which the patient reports typical symptoms of hypoglycemia, and interprets the symptoms as indicative of hypoglycemia, but with a measured plasma glucose concentration >70 mg/dL (3.9 mmol/L).

Pseudo hypoglycemia is identified in e-CRF “Hypoglycemic event” page as those documented as,

- To the question “Countermeasure Administration”, Do NOT tick the option “Subject was Not Capable of Treating Self and Required Assistance”
- To the question “Were Symptoms Present”, ticked “Yes”, and
- With a plasma glucose value before countermeasure >70 mg/dL (3.9 mmol/L).

Probable symptomatic hypoglycemia

Probable symptomatic hypoglycemia is an event during which symptoms of hypoglycemia are not accompanied by a plasma glucose determination, (but that was presumably caused by a plasma glucose concentration \leq 70 mg/dL (3.9 mmol/L)), i.e., symptoms treated with oral carbohydrate without a test of plasma glucose.

Probable symptomatic hypoglycemia is identified in e-CRF “Hypoglycemic event” page as those documented as,

- To the question “Countermeasure Administration”, the option “Subject was Not Capable of Treating Self and Required Assistance” not ticked, and
- To the question “Were Symptoms Present”, ticked “Yes”, and
- With no plasma glucose value before countermeasure, and
- To the question “Did this countermeasure lead a significant improvement or prompt recovery?” ticked “Yes”.

Any hypoglycemic event fulfilling the criteria of a SAE or leading to unconsciousness, coma, or seizure will also be recorded as a SAE. Only hypoglycemia events fulfilling the criteria of an SAE will also be documented on AE and SAE complementary forms in the eCRF.

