2.4.5.1 Hypoglycemia

Analyses of hypoglycemia will be performed on the TEAE period as defined in [Section 2.1.4](#). Hypoglycemia will be classified as severe hypoglycemia, documented hypoglycemia (blood glucose ≤ 70 mg/dL and < 54 mg/dL), probable symptomatic hypoglycemia or pseudo hypoglycemia.

The number (%) of patients with at least 1 hypoglycemia, severe hypoglycemia and documented hypoglycemia (blood glucose ≤ 70 mg/dL and < 54 mg/dL), probable symptomatic hypoglycemia or pseudo hypoglycemia will be summarized respectively by treatment group during the TEAE period, as well as the incidence rate in patient years. Two types of incidence rates will be presented: the number of patients with at least 1 event per patient-year (calculated as the number of patients with at least 1 event / total exposure in patient-year), and the number of events per patient-year (calculated as the total number of events / total exposure in patient-years). Note: here exposure (in days) is the duration of TEAE period, i.e., duration of IMP treatment in days +1 (see [Section 2.1.4](#)).

A KM curve will also be provided by treatment group for the time to first severe hypoglycemia or documented hypoglycemia during the TEAE period for the entire 26-week treatment period only.

A listing of patients for all events reported on the dedicated e-CRF “Hypoglycemic event information” page will be provided with each category flagged (i.e., severe hypoglycemia, documented hypoglycemia, probable symptomatic hypoglycemia and pseudo hypoglycemia).

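### The eCRF rule for severe hypoglycemia requires symptoms to be ticked Yes, a condition absent from the SAP's own definition, so some assisted events drop out of the severe category

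*SAP*

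**What the plan says.** Section 2.1.4.1 first defines the category in words: "Severe hypoglycemia is an event requiring assistance of another person to actively administer carbohydrate, glucagon, intravenous glucose or other resuscitative actions". It then describes what may accompany such an event: "These episodes may be associated with sufficient neuroglycopenia to induce seizure, unconsciousness or coma". On glucose it says "Plasma glucose measurements may not be available during such an event", and adds that "neurological recovery attributable to the restoration of plasma glucose to normal is considered sufficient evidence that the event was induced" by low glucose. None of these three statements makes a symptom answer a condition.

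The identification rule on the hypoglycemic event page follows at once and has two parts joined by a conjunction. The first concerns the countermeasure item: "ticked the option “Subject was Not Capable of Treating Self and Required Assistance”, and". The second is "To the question “Were Symptoms Present”, ticked “Yes".

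The other categories in the same section work as follows:

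- Documented hypoglycemia needs a glucose value before countermeasure of 70 mg/dL or below, or below 54 mg/dL. It has no condition on symptoms or assistance.
- Pseudo hypoglycemia needs the assistance option not ticked, symptoms Yes, and glucose above 70 mg/dL.
- Probable symptomatic hypoglycemia needs the assistance option not ticked, symptoms Yes, no glucose value, and significant improvement or prompt recovery.

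Section 2.4.5.1 reports the number (%) of patients with any hypoglycemia and with each named category, two incidence rates per patient-year, and a listing of all events on the dedicated page with category flags. It also plans a curve: "A KM curve will also be provided by treatment group for the time to first severe hypoglycemia or documented hypoglycemia".

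**The concern.** The definition and the rule that is meant to implement it select different sets of events. The definition turns on assistance alone; the rule takes only the assisted events that also have symptoms ticked Yes. The programmer will follow the rule, so the tables will report a narrower category than the one the SAP defines.

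The added condition can only lower the severe count. Pseudo and probable symptomatic hypoglycemia both exclude events for which "Subject was Not Capable of Treating Self and Required Assistance" was ticked, so neither can pick up an assisted event that fails the severe rule. Section 2.5.2 handles missing dates for hypoglycemia but gives no specific rule for a blank symptoms answer.

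Severe hypoglycemia is a central safety category when an insulin-containing product is compared with insulin. Section 2.4.5 also reports safety by ethnic/racial subgroup, where one patient weighs more than in the overall arms.

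**Working it through.** No stated figure has to be reproduced. The check applies each category rule of Section 2.1.4.1 to every possible answer pattern on the form.

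**Inputs.** Assistance option (ticked or not, 2 levels); symptoms (Yes, No, blank, 3 levels); glucose before countermeasure (<54, 54 to 70, >70 mg/dL, not measured, 4 levels); prompt recovery (Yes, or No/blank, 2 levels). The item asking whether any event occurred is taken as Yes.

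**Count of patterns.** 2 × 3 × 4 × 2 = 48 in all. With assistance ticked: 3 × 4 × 2 = 24.

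**Assisted events under the rules as written.** Prompt recovery does not change the result here, so its two levels are combined in each row.

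| Symptoms | Glucose (mg/dL) | Named category | Patterns |
|---|---|---|---|
| Yes | any, or not measured | Severe (also documented if ≤70) | 1 × 4 × 2 = 8 |
| No or blank | <54 | Documented at both cut-offs only | 2 × 1 × 2 = 4 |
| No or blank | 54 to 70 | Documented at ≤70 only | 2 × 1 × 2 = 4 |
| No or blank | >70 | None | 2 × 1 × 2 = 4 |
| No or blank | Not measured | None | 2 × 1 × 2 = 4 |

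Of the 24 assisted patterns, 4 + 4 + 4 + 4 = 16 fail the severe rule although the definition covers them. Of those 16, 8 are documented only and 8 fall in no named category. These are counts of answer patterns, not expected frequencies.

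**Effect by output in Section 2.4.5.1.**

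- Severe number (%) and both severe rates: the event is absent in all 16 patterns.
- Kaplan-Meier curve: the 8 patterns with glucose ≤70 mg/dL still enter as documented hypoglycemia; the 8 with glucose >70 mg/dL or no value do not.
- Any-hypoglycemia count and listing: all 16 patterns are present, because Section 2.1.4.1 identifies hypoglycemia as any event on the dedicated page.

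**With severe derived from the assistance option alone.** All 24 assisted patterns are severe, so those missed go from 16 to 0 and the assisted patterns in no category go from 8 to 0. Nine non-assisted patterns remain without a named category either way.

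**Scale.** Section 1.3 gives 120 patients per treatment. One patient is 1/120 = 0.83 percentage points of an arm, if all 120 are treated.

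**The case against.** The strongest reply is that the affected cell may be nearly empty. A patient who cannot treat himself or herself will normally have symptoms. The form asks whether symptoms were present, not whether the patient reported them, so a site need not answer No for an unconscious patient. The reference to neurological recovery also presupposes impairment. A No on an assisted event may be a data inconsistency, and a blank may be queried before lock. Completion guidance may sit in the protocol, to which the section refers. All of this bears on how often the problem occurs, and it stands. It does not reconcile the two statements: if symptoms are always ticked Yes, the condition is redundant, and if not, it removes events that meet the definition.

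A reader might infer three stronger things that the SAP does not support.

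- That these events disappear from reporting. They do not: the any-hypoglycemia count and the flagged listing keep them, and Section 2.1.4.1 has events that meet SAE criteria or lead to unconsciousness, coma or seizure recorded as SAEs. What remains is that the severe rows are not corrected by these outputs, and that a non-serious assisted event has no AE form behind it, because only hypoglycemia meeting SAE criteria goes there.
- That the rule also errs the other way, by counting as severe an assisted, symptomatic event with glucose above 70 mg/dL. Under a definition that rests on assistance, such an event is severe in both the definition and the rule, so there is no mismatch.
- That the severe count would be materially understated, for instance halved. The SAP gives no expected number of severe events or of affected answers, so no such figure can be given.

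The trial is now descriptive, with no systematic safety testing planned. That lowers the stakes, but the descriptive counts are then the result itself.

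**Conclusion.** The point holds as a contradiction inside Section 2.1.4.1: the identification rule carries a symptoms condition that the definition does not have. Applied literally, it excludes assisted events with symptoms No or blank from the severe number (%) and both severe rates. Those without a low glucose reading also leave the Kaplan-Meier curve.

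The direction is certain, since the condition can only reduce the severe count. The size is unknown and may be small. The patient-level percentage changes only for a patient with no other qualifying severe event, and the curve only where the dropped event would have been that patient's first. The conclusion assumes that the rules are programmed as written and that no completion or query rule outside the SAP forces the symptoms answer to Yes on assisted events.

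**What to change.** Reconcile the identification rule with the SAP's own definition by deriving severe hypoglycemia from the assistance option and removing the symptoms condition. At minimum, state that a No or blank symptoms answer does not remove an assisted event from the severe category.

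In the listing already planned, flag assisted events with symptoms No or blank, and assisted events with glucose above 70 mg/dL, so that a reader can judge them individually. An additional table row for events in no named category is optional; it would also show the non-assisted patterns that have none.

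The cost is one derivation line and a listing flag before database lock, on data the eCRF already collects. The small downside is that the severe count may rise slightly, possibly through events whose symptoms answer is simply a data error; the flag makes those visible.
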